12.4 Follow-up of Adverse Events and Serious Adverse Events

AEs that occur following receipt of a single vaccination are followed until the final outcome is known or until the end of the study follow-up period.

SAEs that have not resolved by the end of the follow-up period will be followed until final outcome is known. If it is not possible to obtain a final outcome for an SAE (e.g., the subject is

lost to follow-up), the last known status and the reason a final outcome could not be obtained will be recorded by the investigator on the AE CRF (if the CRF is still open) and by REDCap or on the Safety Expedited Report Form (SERF).

12.5 Investigator Reporting Responsibilities to the Sponsor

12.5.1 Adverse Events

AE data will be entered into the research database no less than every other week and will include all data through one week prior to database entry. Line listings, frequency tables and other summary AE data will be submitted to the IND sponsor when requested for periodic safety assessments, review of IND Annual Reports, review of IND Safety Reports, and preparation of final study reports.

12.5.2 Serious Adverse Events

All SAEs (regardless of relationship and whether or not they are also UPs) must be reported by REDCap or on the SERF and sent to the CSO by fax or email attachment. Deaths and immediately life-threatening SAEs must be reported to the CSO within 1 business day after the site becomes aware of the event. All other SAEs must be reported within 3 business days of site awareness.

CSO CONTACT INFORMATION:

Clinical Safety Office [name] [name] 21704

[contact] [contact]

E-mail: [contact]

https://crimsonredcap.cc.nih.gov/redcap/index.php

SAEs that occur after the final study visit that are reported to and are assessed by the investigator to be possibly, probably, or definitely related to study drug must be reported to the CSO.

The clinical site investigator in Mali will also notify LMIV PI and the ISM in Mali by email, fax, or telephone within 1 working day of notification of an SAE occurrence.

LMIV Contact Information:

[name] [contact]

[contact]

Email: [contact]

12.5.3 Unanticipated Problems

Unless otherwise specified above, UPs that are also AEs or SAEs, must be reported to the CSO (by REDCap, or by email and SERF if REDCap is not available) no later than when they are due to be reported to the FMPOS EC.

UPnonAEs are not reported to the CSO but must be reported to the clinical trials management (CTM) group and the EC according to their requirements and preferred methods. If the UPnonAE raises a significant potential subject safety concern, the SMM should be consulted by email or phone no later than when reports are made to the EC and/or CTM.

12.5.4 Pregnancy

Pregnancy itself is not an AE. However, complications of pregnancies are AEs and may be SAEs. Events that meet AE or SAE criteria in relation to pregnancy, delivery, or the conceptus/neonate (see Section 12.1) are reportable (by REDCap, or by email and SERF if REDCap is not available). All pregnancies occurring up until 1 month after last vaccination will be reported (by REDCap, or by email and SERF if REDCap is not available) to the CSO within 1 business day from site awareness. Pregnancies after that timepoint will be reported in a non-expedited manner.

Pregnancy outcome data (e.g., delivery outcome, spontaneous or elective termination of the pregnancy) will be reported to the CSO (by REDCap, or by email and SERF if REDCap is not available) and LMIV within 3 business days of the site's awareness.

In the event of pregnancy in a study subject who has possibly been exposed to study agent, the following steps will be taken:

- Unblind the study subject
- Discontinue the study agent.
- Discuss with women who become pregnant continued participation in the study, including continued safety/research labs (at investigator's discretion given blood volumes) and clinical visits.
- Report to FMPOS EC as an informational item.
- Report to the DSMB, SMM, and Malian ISM.
- Advise research participant to notify the obstetrician of study participation and potential study agent exposure.

12.5.5 Medically Attended Adverse Events (MAAEs) that are Potential Immune-Mediated Medical Conditions (PIMMCs)

This trial includes plans for collection and analysis of data relating to medically attended adverse events (MAAEs) among subjects in all treatment groups through 12 months following the last study vaccination, due to the theoretical potential for induction of autoimmune or autoinflammatory diseases due to Matrix-M.

Collection of MAAE data beyond 6 months after the last study vaccination will not delay submission of clinical trial reports and initiation of subsequent clinical trials. Final analyses of MAAEs will be submitted in clinical trial report addenda.

As part of our analyses of MAAEs in all annual reports, clinical trial reports, and clinical trial report addenda, we will include tabulated summaries of available adverse event data for potentially immune-mediated medical conditions reported during the trial, categorized by MedDRA term. These summaries will include any MedDRA preferred term included in the Immune-mediated/Autoimmune disorders Standard MedDRA Query (SMQ). Conditions reported during the trial that match the terms included in the SMQ (or list of terms provided by FDA) as well as any other potentially immune-mediated medical conditions reported during the trial that do not appear in the SMQ will be included. For each adverse event included in the summaries, we will provide a case narrative, along with an assessment of the seriousness of the event and causal relationship to study vaccine, as required by 21 CFR 312.32.

Because the request for this information by the FDA is based on a theoretical potential, the occurrence of a potentially vaccine-related immune-mediated medical condition will be considered unexpected. We will adhere to expedited reporting requirements as provided in 21 CFR 312.32 for any adverse event assessed as a serious and unexpected suspected adverse reaction (SUSAR).

Based on the theoretical concern for the development of autoimmune diseases after vaccination with new vaccines containing novel adjuvants, a list of Adverse Events of Special Interest (AESI) specific to potential immune-mediated medical conditions (PIMMCs) is provided in Appendix D (Integrated Summary of Safety of Other Novavax Recombinant Nanoparticle Vaccine Antigens with Matrix-M1TM Adjuvant, Version 1.0 dated 20 April 2021).

Reporting of MAAEs (which are PIMMCs) to the CSO will be included in monthly safety reports (in separate table[s]) unless they are considered to be SAEs, in which case they will be reported to the CSO as per Section 12.5.2 (SAE Reporting).

In order to be certain that the study team is alerted to any PIMMCs as quickly as possible, study participants will be asked to report to the study team for any medical issues which arise from the

start of the study through 12 months after the final dose. They will also be asked to provide information about any Medically Attended Adverse Events (MAAEs) where the participant was seen by a Health Care Provider outside of the study (including visits to doctors, nurse practitioners, traditional healers and any other local practitioners). In this way, the study team can determine if any of these complaints may be considered PIMMCs.

12.6 Investigator Reporting Procedures to FMPOS

12.6.1 Definitions

Protocol Deviation: Any change, divergence, or departure from the EC-approved research protocol.

- **Major Deviations:** Deviations from the EC-approved protocol that have, or may have the potential to, negatively impact, the rights, welfare or safety of the subject, or to substantially negatively impact the scientific integrity or validity of the study.
- **Minor Deviations:** Deviations that do not have the potential to negatively impact the rights, safety, or welfare of subjects or others, or the scientific integrity or validity of the study.

Non-Compliance: Failure of investigator(s) to follow the applicable laws, regulations, or institutional policies governing the protection of human subjects in research, or the requirements or determinations of the EC, whether intentional or not. Failure of subjects to comply with the research protocol does not represent non-compliance unless that failure is due to an action or omission of a member of the research team, for example, the failure to give adequate instruction to the subject.

- Serious non-compliance: Non-compliance, whether intentional or not, that results in harm or otherwise materially compromises the rights, welfare and/or safety of the subject. Non-compliance that materially affects the scientific integrity or validity of the research may be considered serious non-compliance, even if it does not result in direct harm to research subjects.
- Continuing non-compliance: A pattern of recurring non-compliance that either has resulted, or, if continued, may result in harm to subjects or otherwise materially compromise the rights, welfare and/or safety of subjects, affect the scientific integrity of the study or validity of the results. The pattern may comprise repetition of the same non-compliant action(s), or different noncompliant events. Such non-compliance may be unintentional (e.g. due to lack of understanding, knowledge, or commitment), or intentional (e.g. due to deliberate choice to ignore or compromise the requirements of any applicable regulation, organizational policy, or determination of the EC).

12.6.2 Expedited Reporting to FMPOS EC

Non-compliance: Any actual or suspected non-compliance by any investigator or entity associated with the protocol must be reported by the Malian PI/designee within 7 calendar days of any investigator or individual associated with the protocol first becoming aware, unless otherwise indicated in this policy. Non-compliance will be reported to the NIH Office of Human Subjects Research Protections as required per institutional policy.

Major Deviation: A deviation must be reported within 7 calendar days of an investigator becoming aware of an actual or suspected deviation. Although protocol deviations are also non-compliance, these should only be reported once as deviations.

UP: A UP must be reported within 7 calendar days of an investigator becoming aware of the actual or suspected UP.

Death: Any death of a research subject that is possibly, probably or definitely related to the research must be reported within 24 hours of an investigator becoming aware of the death.

New information: New information that might affect the willingness of a subject to enroll or remain in the study should be reported within 7 calendar days of an investigator first becoming aware.

Suspension or termination of activities: Any suspension or termination of research activities, including holds on new enrollment, placed upon the research by the study sponsor, NIH or ethical review committee leadership, or any regulatory agency must be reported within 7 calendar days of an investigator becoming aware.

12.6.3 Annual Reporting to FMPOS EC

Investigators must provide the following information to the EC in summary format at the time of continuing review: minor protocol deviations; AEs and SAEs that do not meet the definition of an UP.

12.7 Sponsor's Reporting Responsibilities

Events reported to the sponsor will be promptly evaluated and will be reported as required according to FDA IND safety reporting guidance and regulations. IND safety reports will be shared with other stakeholders according to applicable agreements (e.g., CRADAs and CTAs).

The IND sponsor will also submit an IND Annual Report of the progress of the investigation to the FDA as defined in 21 CFR 312.33.

12.8 Pausing Rules for the Protocol

Pausing is the suspension of administration of study agent to a single subject until a decision is made whether or not to resume administration of the study agent.

12.8.1 Pausing Rules for an Individual Subject

The pausing criteria for a SINGLE subject in this study include any of the following:

- A subject experiences one SAE that is determined as possibly, probably, or definitely related to a study agent
- A subject experiences a hypersensitivity reaction (e.g. anaphylaxis, diffuse urticaria) that is determined to be possibly, probably, or definitely related to the vaccine
- A subject experiences ≥1 Grade 3 or greater AEs or ≥1 Grade 3 laboratory abnormalities that are deemed not to be a SAE (solicited local/systemic or unsolicited; lasting 72 hours or more) that are possibly, probably, or definitely related to a study agent, within the 7 days post vaccination
- Any safety issue that the site investigator determines should pause administration of a study agent to a single subject.

The CSO, in collaboration with the PI, may also pause for an individual subject for any safety issue. The study safety oversight bodies (i.e., DSMB and/or ISM) may recommend a pause to the PI.

12.8.2 Reporting a Pause

If a pausing criterion is met, a description of the AE(s) or safety issue must be reported by the PI within 1 business day to the CSO and to the FMPOS EC according to their requirements. The PI will also notify the DSMB and ISM through the specified pathway.

12.8.3 Resumption of a Paused Study

The CSO, in collaboration with the PI, DSMB, and ISM, will determine whether or not it is safe to resume administration of the study agent to the subject. The PI will notify the FMPOS EC of the decision on resumption of the study agent. A subject who does not resume study agent administration will continue to be followed for safety and may provide samples for immunology assays.

12.9 Halting Rules for the Protocol

Halting the study requires immediate discontinuation of study agent administered for all subjects and suspension of enrollment until a decision is made whether or not to continue enrollment and study agent administration.

The following criteria will be used to define unacceptable reactogenicity of the malaria vaccine (AEs that are possibly, probably, or definitely related to the vaccine will be considered "related" and will be summarized as such):

- 1 or more subject(s) experience an SAE as defined in Section 12.1 of this protocol that is determined to be possibly, probably, or definitely related to the vaccine, **or**
- 1 or more subjects experience a hypersensitivity reaction (e.g. anaphylaxis, diffuse urticaria) that is determined to be possibly, probably, or definitely related to the vaccine, or
- Pilot Group: > 20% (2 or more of n=5) of vaccinees assigned to an experimental vaccine dosage (either low, middle or high dose) experience any Grade 3 AE (solicited or unsolicited) lasting 48 hours or more or any Grade 3 laboratory abnormality with either the AE or lab abnormality determined to be possibly, probably, or definitely related to the vaccine as defined in this protocol, within the 7 days post vaccination
- Main Group*: ≥20% (4 or more of n=20) of vaccinees assigned to an experimental vaccine dosage (either low, middle or high dose) experience any Grade 3 AE (solicited or unsolicited) with signs or symptoms lasting for 48 hours or more or any Grade 3 laboratory abnormality with either the AE or lab abnormality determined to be possibly, probably, or definitely related to the vaccine as defined in this protocol, within the 7 days post vaccination

or

• Any safety issue that the study PI or CSO determines should halt the study.

*Once the Main Group starts, Halting Rules will be based on review of data from all 20 participants receiving a specific experimental vaccine dosage (n=20)

If halting criteria are met based on blinded data, the list of research participants with the Grade 3 AEs or laboratories will be sent to the DSMB Executive Secretary. A DSMB Meeting could be convened on short notice at the occurrence of such an event.

In addition, the FDA, FMPOS EC and/or CSO may halt the study at any time.

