3.1.1 Safety of Pfs230D1M-EPA/Alhydrogel in Healthy Adults

In both the US and Mali, Pfs230D1M-EPA/Alhydrogel vaccinations at increasing doses were well-tolerated, with minimal local and systemic reactogenicity. The majority of the reported AEs were mild (Grade 1) or moderate (Grade 2). Safety analysis of the high dose (40 µg) of

^A Arms that received the full 4-dose regimen (initial series + booster) during the vaccine activity phase (main) of the Mali study.

[figure not shown]
Pfs230D1M-EPA/Alhydrogel showed that many reported AEs were mild (Grade 1; 708/1431; 49%), with the most commonly reported AEs being injection site pain, headache, malaria, neutropenia, nasopharyngitis, and rhinitis. The majority of laboratory abnormalities were Grade 1. The most commonly reported related AEs were injection site reactogenicity (pain, induration, pruritus, and edema), leukopenia, neutropenia, and headache, which were all Grade 1 or 2. The related AE reported with the highest frequency was injection site pain, which did not increase in frequency with subsequent vaccination. However, overall, reported local reactogenicity, but not solicited systemic symptoms, appeared to increase (in frequency and duration of symptoms) with increasing antigen dose of Pfs230. In comparison to the comparator arms, more related AEs were reported for the Pfs230D1M vaccinees, alone or in combination, and the majority of these were Grade 1 or 2 local reactogenicity.

In a single Pfs230-vaccinated subject in Mali, a Grade 3 gastroenteritis was reported with associated Grade 4 laboratory abnormalities (leukocytosis, increased blood creatinine), all deemed unlikely related to vaccination and all of which resolved shortly after resolution of the gastroenteritis symptoms. Other than this case, there were no Grade 3 or 4 AEs. There were 3 unrelated SAEs, one of which was a cerebrovascular accident that led to death. No SAEs were reported in the Pfs230-vaccinated arms. No participants were removed from study participation due to a related AE of any severity.

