pain, which was observed in about half of Pfs230D1M vaccinees. Of the related Grade 2 AEs, injection site pain was most common (7/11, 63%) followed by headache, fatigue, and injection site movement impairment in one subject. There were no related Grade 3 AEs. Participants in the Pfs230D1M booster arm experienced significantly more Grade 1 injection site pain and headache than the comparator arm. Grade 2 injection site pain was also reported more frequently in the Pfs230D1M arm but was not significantly different from the comparator.

[figure not shown]
3.2.2 Immunogenicity and Functional Activity (SMFA) of Pfs230D1M-EPA/AS01 in Healthy Adults (Primary Series + 4th Dose; Year 1 + 2)

Vaccination induced detectable antibody titers 2 weeks after the first dose, which increased further after dose 2, but the peak after a third dose was not significantly higher (Figure 11). There were no differences in titers between the low and high vaccine doses. Antibody function was assessed 2 weeks and 12 weeks after dose 2 (Figure 12). Anti-Pfs230 was sufficient to induce 100% TRA 2 weeks post dose 2, which was still >90% 12 weeks post dose 2. In contrast, anti-Pfs25 did not exceed 80% TRA post dose 2. The combination of Pfs25 and Pfs230 was not superior to Pfs230 alone for inducing functional serum activity.

Figure 11. Antibody Responses to Pfs230D1M-EPA/AS01 after Low Dose and High Dose Vaccinations of Adults in Sotuba, Mali during Pilot Phase trial.

[figure not shown]
A Low Dose Groups

B High Dose Groups

Response assessed by enzyme-linked immunosorbent assay (ELISA). (A) shows antibody responses of Malian adults after administration of low-dose vaccinations of Pfs230D1M-EPA/AS01 (either 13 μg Pfs230D1M alone or 16 μg Pfs230D1M-EPA/AS01 plus Pfs25M) at various time points out to 6 months. (B) shows antibody responses after administration of high-dose vaccinations of Pfs230D1M-EPA/AS01 (either 40 μg Pfs230D1M alone or 47 μg Pfs230D1M-EPA/AS01 plus Pfs25M) at various timepoints out to 6 months. Red arrows indicate immunization administrations at 0, 1, and 6 months. Dotted lines represent antibody titers to Alhydrogel-adjuvanted Pfs230D1M-EPA obtained in previous studies.

Figure 12. Antibody Function by Standard Membrane Feeding Assay to Pfs230D1M-EPA/AS01 after Low-Dose and High-Dose Vaccinations of Adults in Sotuba, Mali during Pilot Phase trial.

[figure not shown]

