- is a congenital anomaly/birth defect/miscarriage/stillbirth NOTE: This definition is more inclusive than some commonly published definitions. It includes an affected conceptus/neonate whose:
- biological mother was exposed to a study agent at any point from conception through the end of the pregnancy, and/or, if breastfeeding, the 30-day neonatal period; or

- biological father was exposed to a study agent at any point during the 90 days prior to conception.
- This is separate from, and in addition to, general reporting of pregnancy in a study participant or female partner of a male participant (see Section 12.5.4 below).
- a medically important event NOTE: Medical and scientific judgment should be exercised. Events that significantly jeopardize the subject and/or require intervention to prevent one of the SAE outcomes listed above are generally considered medically important, and are thus SAEs.

Unexpected AE: An AE is unexpected if it is not listed in the investigator's brochure or package insert (for marketed products) at the frequency, specificity, and severity that has been observed.

NOTE:

- o Such events should also be evaluated for possible reporting as unanticipated problems (UPs) (see Section 12.5.3 below).
- o Unexpected, as used in this definition, also refers to AEs or SARs that are mentioned in the investigator's brochure as occurring with a class of drugs/biologics, or as anticipated from the pharmacological properties of the study agent but are not specifically mentioned as occurring with the particular study agent under investigation.

Serious and Unexpected Suspected Adverse Reaction (SUSAR): A SUSAR is an SAR (defined above) that is both serious and unexpected.

UP: A UP is any event, incident, experience, or outcome that is

- unexpected in terms of nature, severity, or frequency in relation to
 - the research (including but not limited to risks) as described in the EC-approved research protocol and informed consent document, investigator's brochure, or other study documents; and
 - o the characteristics of the subject population being studied; and is
- possibly, probably, or definitely related to participation in the research; and
- suggests the research places subjects or others at a greater risk of harm (including physical, psychological, economic, or social harm) than was previously known or recognized, per the documents currently approved by the EC.

NOTE:

- o Per the sponsor, an SAE always meets this "greater risk" criterion.

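### The numeric halting counts in 12.9 say Grade 3 without 'or greater', and three Appendix B cells leave worse values ungraded, so on a literal reading some worse non-SAE events do not count

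*Combined protocol and SAP*

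**What the plan says.** Section 12.9 has two numeric criteria, each applied per experimental dose level and limited to related events within 7 days of vaccination.

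- Pilot Group, 2 or more of 5 vaccinees: "experience any Grade 3 AE (solicited or unsolicited) lasting 48 hours or more or any Grade 3 laboratory abnormality".
- Main Group, 4 or more of 20 vaccinees: "experience any Grade 3 AE (solicited or unsolicited) with signs or symptoms lasting for 48 hours or more or any Grade 3 laboratory abnormality".

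If a criterion is met on blinded data, "the list of research participants with the Grade 3 AEs or laboratories will be sent to the DSMB Executive Secretary". All three places name Grade 3 only.

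The individual pausing rule in 12.8.1 is worded differently: "A subject experiences ≥1 Grade 3 or greater AEs or ≥1 Grade 3 laboratory abnormalities that are deemed not to be a SAE". There the wider phrase is attached to AEs but not repeated for laboratory values.

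Section 12.9 also halts the study for one related SAE, for one related hypersensitivity reaction, or for any safety issue at the discretion of the PI or the Clinical Safety Office (CSO). Grades come from Appendix B. Table 10 in 12.3.1 is the fallback, but only for AEs that the appendices do not list.

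**The concern.** The count is the only numeric halting trigger for severe related events that are neither SAEs nor hypersensitivity reactions. Such a trigger should not become less sensitive as severity rises. As worded, an event can leave the count by being worse, either because it reaches Grade 4 or because it falls into a gap in the laboratory table. Since 12.8.1 uses the wider phrase for AEs, a literal reader of 12.9 has a textual reason to exclude Grade 4. What is at stake is whether a first-in-human rule with five vaccinees per pilot dose fires when it should. No analysis or estimate is affected.

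**Working it through.** **Thresholds.** More than 20% of 5 means more than 1, so 2. At least 20% of 20 means at least 4. Both match 12.9.

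**Appendix B, laboratory table for Malian adults.** Each of the nine rows was checked for a value beyond the Grade 3 range with no fever, dialysis or transfusion.

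| Row | Grade 3 | Grade 4 | Value beyond Grade 3 alone |
|---|---|---|---|
| Hemoglobin, male | 6.5–7.9 | < 6.5 and/or transfusion | Grade 4 |
| Hemoglobin, female | 6.0–6.9 | < 6 and/or transfusion | Grade 4 |
| WBC increase | 20.1–25.0 | > 25.0 | Grade 4 |
| WBC decrease | 1.0–1.4 | < 1.0 with fever | **no grade** |
| Neutrophil decrease | < 0.50 | < 0.50 with fever | Grade 3 |
| Platelets | 25–69 | < 25 | Grade 4 |
| Creatinine, male | 177.00–221.00 | > 221.00 and dialysis | **no grade** |
| Creatinine, female | 160.00–215.99 | > 216.00 and dialysis | **no grade** |
| ALT | 301.0–600.0 | > 600.0 | Grade 4 |

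Three rows have a gap. A male creatinine of 200 µmol/L is Grade 3 and counts; 230 without dialysis has no tabulated grade. The WBC gap matters only when neutrophils are still at least 0.50, because below that the neutrophil row already gives Grade 3 without fever.

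**Effect on the count, with no rate assumed.**

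- Pilot dose group with one related Grade 3 value and one related ALT above 600 that is not an SAE: literal count 1 of 5, no trigger; with *Grade 3 or greater*, 2 of 5, trigger.
- Main dose group with four subjects who have only such Grade 4 or untabulated values: literal count 0 of 20; corrected count 4 of 20.

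**Illustration of the change in probability.** Let p be the per-subject rate of related qualifying events of Grade 3 or worse. Let f be the share of those subjects whose only qualifying events are non-SAE Grade 4 or untabulated. The literal rule sees p(1 − f), so the chance of reaching the trigger is P(X ≥ 2) with n = 5, or P(X ≥ 4) with n = 20, X binomial with that probability. Neither p nor f is given in the documents.

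| p | f | p(1 − f) | Pilot | Main |
|---|---|---|---|---|
| 0.05 | 0 | 0.050 | 0.0226 | 0.0159 |
| 0.05 | 0.10 | 0.045 | 0.0185 | 0.0111 |
| 0.10 | 0 | 0.100 | 0.0815 | 0.1330 |
| 0.10 | 0.10 | 0.090 | 0.0674 | 0.0993 |

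At p = 0.05 the loss is 0.0041 (pilot) and 0.0048 (main). At p = 0.10 it is 0.0141 and 0.0337.

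Prior experience points to the lower rate. Section 3.1.1 reports no related Grade 3 or 4 AE with the Alhydrogel formulation. For 0 of the 50 Malian subjects at 40 µg (Table 3), the one-sided 95% upper limit is 1 − 0.05^(1/50) = 0.058. After the AS01 booster, 3.2.1 states: "There were no related Grade 3 AEs". The adjuvant here is different, so this is only a guide.

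**The case against.** The strongest reply is that few related Grade 4 events would escape a halt, and that those few would be seen.

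- **SAE overlap.** Most Grade 4 symptom cells in Appendix B require an ER visit or hospitalization, and required hospitalization is an SAE. Grade 4 in Table 10 describes treatment needed to prevent death. Grade 4 creatinine requires dialysis. Section 12.1 adds: "Events that significantly jeopardize the subject and/or require intervention to prevent one of the SAE outcomes listed above are generally considered medically important", and such events are then SAEs. This stands. It leaves mainly isolated laboratory values (ALT > 600, platelets < 25) and ER-only visits for an AE lasting 48 hours.
- **Timing.** Apart from the vaccination-day sample, safety laboratory tests within 7 days of a dose are scheduled only on Days 4, 32 and 60. This stands and narrows the exposure.
- **Oversight.** Section 12.2 has the PI review all abnormal laboratory findings routinely, the discretionary halt remains, and the DSMB must concur before the Main Group starts (1.2.1). This stands, but it relies on judgement, which a numeric trigger is meant to supplement.
- **Untabulated values.** Section 12.2 and footnote 1 of the laboratory table leave room for investigator grading. This stands in part: Table 10 is reserved for AEs not listed in the appendices, and WBC and creatinine are listed.

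A reader might also infer that a Grade 4 laboratory value escapes the individual pause in 12.8.1. The documents do not support that. Section 12.1 defines AEs to include laboratory findings, and 12.3 speaks of graded laboratory AEs. A tabulated related Grade 4 value lasting 72 hours or more is therefore already covered by the AE part of that rule, which moreover contains no count.

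**Conclusion.** The point holds as a minor wording defect in a decision rule. On a literal reading, the counts in 12.9 exclude related Grade 4 and untabulated events that are neither SAEs nor hypersensitivity reactions. The intent was very probably *Grade 3 or greater*, and sites may apply it that way.

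The change in the chance of reaching the trigger is about half a percentage point at p = 0.05 and f = 0.10. It rests on an assumed f with no support in the documents, and it concerns this trigger alone, not the overall chance of a halt.

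Two stronger conclusions should not be drawn. First, a reader might take the earlier trial as proof that a Grade 4 event without SAE status has already slipped through. Section 3.1.1 reports "a Grade 3 gastroenteritis was reported with associated Grade 4 laboratory abnormalities (leukocytosis, increased blood creatinine), all deemed unlikely related to vaccination" and also "No SAEs were reported in the Pfs230-vaccinated arms". That event was judged unlikely related, so it would not have counted under any wording, and the earlier trial's grading table and SAE definition are not in these documents. Second, a reader might infer that serious related toxicity could build up without a halt. One related SAE is enough to halt the study.

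**What to change.** 1. In both numeric criteria of 12.9 and in the sentence on the list sent to the DSMB, write *Grade 3 or greater* for AEs and for laboratory abnormalities.
2. Make the three Appendix B cells contiguous. Either define Grade 4 as creatinine > 221.00 (male) or ≥ 216.00 (female) *and/or* requiring dialysis, and WBC < 1.0 with or without fever; or extend Grade 3 to those values when dialysis or fever is absent. The sponsor's medical monitor should choose.
3. Use the same phrase for laboratory values in 12.8.1, for consistency only.

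The cost is a few words and three table cells in an amendment, with a slightly higher chance of a halt. The thresholds of 2 of 5 and 4 of 20 do not change.
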